9.1.1.6 Clinic Visit 4: Day 57 (-3/+7 days)

- Review and record any newly reported safety data including unsolicited AEs or other AEs (e.g., medically-attended AEs, SAEs).
- Record concomitant medications and vaccinations according to instructions in Section 7.6.
- Perform a symptom-directed physical examination (at the discretion of the Investigator; see Section 9.3.6).
- Measure vital signs (body temperature, pulse, blood pressure, see Section 9.3.6).
- Collect a blood sample for immunogenicity assessment (see Table 1) for binding antibody testing to RBD of S protein of SARS-CoV-2 (~6 mL blood) and SARS-CoV-2 viral neutralizing activity (~6 mL blood). (No testing of binding antibody to N protein of SARS-CoV-2 will be performed at this time point).
- Instructions for the subject:
 - Inform the subject that reporting of unsolicited AEs is complete.
 - Remind the subject to call the site immediately to report the following:
 - o If he/she experiences any concerning medical event.
 - Any medically-attended visits that are not routine visits for physical examination or vaccination, such as visits for hospitalization, an emergency room visit, or an otherwise unscheduled visit to or from medical personnel (medical doctor) for any reason.
 - Experience a serious medical event, have a change in overall health or be diagnosed with a new medical condition by a doctor. These should be reported regardless of the perceived relationship between the event and the trial vaccine.
 - Remind the subject to contact the site immediately if he/she has any of the symptoms suggestive of COVID-19. In addition, subjects will be messaged up to twice a week to provide a yes or no response to having COVID-19 symptoms. Those who respond "yes" will be contacted by trial staff for follow-up information if the Investigator considers the symptoms could potentially indicate a COVID-19 case (see Section 9.2.1 and Section 9.5).
 - The subject should also be reminded to contact the site immediately if he/she had a positive SARS-CoV-2 test performed outside of the site, whether they were symptomatic (COVID-19 illness) or asymptomatic at the time of the test.
- Complete the source documents and eCRF for this visit.

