9.3.3 Adverse Events

Definitions of AEs/SAEs, procedures for recording, evaluating, follow-up and reporting of AEs/SAEs/pregnancy/overdose, as well as assessments of intensity and causality of AEs, are provided in Appendix 10.

In Phase 2b, any AEs occurring during the 30-minute observation period after vaccination will be recorded in the eCRF. In Phase 3, only those AEs occurring during the 30-minute observation period after vaccination which constitute an AESI, medically-attended AE, or an SAE will be recorded in the eCRF.

It is important to note that COVID-19 illness and its complications/sequelae are consistent with the efficacy endpoints of the trial and, as such, should not be recorded as AEs. These data will be captured on the relevant eCRF pages for cases of COVID-19 illness that occur in the trial, which are expected outcomes of the trial. Only for any complications and sequelae of COVID-19 illness not mentioned on the COVID-19 summary form in the eCRF, an AE form needs to be completed. For consistency, the reporting procedure for COVID-19 cases in the open-label phase will remain as in the randomized observer-blinded phase despite the efficacy analysis is already completed. COVID-19 illness and its complications/sequelae as well as all symptoms listed in Section 9.2.1.4 will not be reported according to the standard expedited process for SAEs, even though the event may meet the criteria for an SAE. However please note that all fatal cases resulting from COVID-19 and its complications/sequelae and from all other events will be reported as SAEs and need to be reported to the CRO within 24 hours (see section Reporting of SAEs in Appendix 10).

Clinical Trial Protocol	CV-NCOV-004
CureVac AG	COVID-19 mRNA Vaccine

The reporting period for each type of AE and corresponding concomitant medication use is shown in Table 6.

АЕ Туре	Days 1 to 8	Days 29 to 36	Days 1 to 57	Day 1 to Month 6 ^a	Day 1 to EOT
Solicited AEs (Phase 2b)	Х	Х			
Unsolicited AEs (Phase 2b)			X		
Medically-attended AEs				Х	
SAE/AESI/COVID-19 fatal cases					Х
Any vaccination other than CVnCoV					Х
Any immune-suppressive/ modulating medication or other prohibited medication					Х
Non-serious intercurrent medical conditions that may affect the immune response to vaccination					Х

 Table 6
 Reporting Period by Type of Adverse Event

AE; adverse event; AESI: AE of special interest; AV: Authorized/licensed vaccines for preventing COVID-19; EOT: End of Trial; SAE: serious AE.

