10.2.2 Safety Analysis Sets 2 (SAS 2, SASsol)

As solicited and unsolicited AEs are collected only for Phase 2b subjects, these analyses will then be restricted to the Phase 2b subjects.

The SAS 2 population will include all Phase 2b subjects of the SAS and will be used for unsolicited AEs analysis.

Clinical Trial Protocol	CV-NCOV-004
CureVac AG	COVID-19 mRNA Vaccine

The SASsol population will include all Phase 2b subjects of the SAS with at least 1 diary collection indicating the occurrence or lack of occurrence of solicited AEs and will be used for solicited AEs analysis.

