9.1.2 Primary Safety Endpoints

All safety endpoints are analyzed in all subjects, in subjects seronegative at baseline, and in subjects seropositive at baseline

- Occurrence, intensity and relationship of medically-attended AEs collected to 6 months after the second trial vaccination in all subjects.
- Occurrence, intensity and relationship of SAEs and AESIs collected through EOT Visit in all subjects.
- Occurrence of fatal SAEs through EOT Visit in all subjects.
- Occurrence, intensity and duration of each solicited local AE within 7 days after each trial vaccination in Phase 2b subjects.

- Occurrence, intensity, and duration of each solicited systemic AE within 7 days after each trial vaccination in Phase 2b subjects.
- Occurrence, intensity and relationship of unsolicited AEs occurring within 28 days after each trial vaccination in Phase 2b subjects.
- Occurrence of AEs leading to vaccine withdrawal or trial discontinuation through to EOT Visit in all subjects.

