10.5 AEs

An AE is any untoward medical occurrence in a subject which does not necessarily have to have a causal relationship with the investigational product. In this trial, confirmed non-fatal cases of COVID-19 and complications/sequelae are not considered as AEs as they are captured on the CRF pages for COVID-19 illness which are expected outcomes of the trial and are analyzed as efficacy endpoints. Only for any complications and sequelae of COVID-19 illness not mentioned on the COVID-19 summary form in the electronic Case Report Form (eCRF), an AE form needs to be completed.

In this trial, for Phase 2b subjects, information on solicited local and systemic AEs occurring within 7 days after each CVnCoV vaccination and on unsolicited AEs occurring within 28 days after each CVnCoV vaccination are collected.

For all Phase 2b and Phase 3 subjects, information on medically attended AEs up to 6 months after second CVnCoV vaccination and SAEs, AESIs and AEs leading to vaccine withdrawal or trial discontinuation after the second CVnCoV vaccination to EOT Visit are recorded.

No other AEs require recording in the CRF.

The recording of AEs remains unchanged, irrespective of the subject rolling over to the OL-phase or not.

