10.5.6 Medically Attended AEs

Up to 6 months after second CVnCoV/placebo vaccination (or up to EOT, whatever is earlier), subjects are asked to confirm if they sought medical attention for an AE. Medically attended AEs are defined as AEs with medically-attended visits that are not routine visits for physical examination or vaccination, such as visits for hospitalization, an emergency room visit, or an otherwise unscheduled visit to or from medical personnel (medical doctor) for any reason. The start of a medically attended AE is defined by its start date, irrespective of the date medical attention was sought. A medically attended AE is considered as occurring up to 6 months after second trial vaccination if

$$\text{Start Date of AE} - (\text{Scheduled date of second vaccination} + 1) \leq 180 \text{ days}.$$

i.e. one month is defined as 30 days and the date of the scheduled second vaccination (Day 29) is used in case a subject only received the first vaccination.

Although the 6 months of medically attended AE recording are not re-started when the subject receives an AV, the subject might have received an AV while still being inside the 6 months window after CVnCoV/placebo administration. Thus the medically attended AEs collected might have been caused by an AV. For details how this is handled in the analyses please see Section 12.7.1.

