12.7 Safety Analyses

12.7.1 Adverse Events

Unsolicited AEs, including SAEs, and AESIs and solicited AEs integrated to or recorded on the CRF are coded using MedDRA Version 23.1 or higher, by SOC and PT.

Only TEAEs as defined in Section 10.5.1 are included in AE summaries. In AE listings, all AEs are included.

Solicited AEs occurring on the day of vaccination and the following 7 days are generally included in summaries if not otherwise stated.

Summaries of medically attended AEs only include those AEs that started up to 6 months after the second trial vaccination, see Section 10.5.6 for further details.

Note that for all summaries by SOC and PT, counting is by subject, not event and subjects are only counted once within each SOC and PT. However, if not stated otherwise, all summaries of unsolicited AEs include the number of AEs reported in each category and all events of a subject are then counted.

All AE summary tables are provided overall, by vaccine group, and by age group and vaccine group and are repeated separately in subjects seronegative at baseline and in subjects seropositive at baseline for SARS-CoV-2 N protein antibody levels (see Section 10.6.1).

In general, percentages are based on the number of subjects in the respective analysis set. In summary tables for AEs after the second vaccination, percentages are based on the number of subjects in the respective analysis set who have received the second vaccination.

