12.7.1.1 Analysis of Unsolicited AEs

The following summaries of unsolicited AEs by SOC and PT are provided, separately for AEs occurring within the first 28 days after each vaccination, within the 28 days after any vaccination, and all reported AEs (including those reported later than 28 days after any vaccination):

- Occurrence of unsolicited AEs,
- Occurrence of related unsolicited AEs,
- Occurrence of unsolicited AEs by maximum severity (mild / moderate / severe),
- Occurrence of related unsolicited AEs by maximum severity (mild / moderate / severe)

Additionally, a summary of unsolicited AEs (excluding solicited AEs) occurring within the first 28 days after each vaccination and within 28 days after any dose that have a frequency of > 5% in at least one treatment arm (on PT level) by SOC and PT is provided. The summary is repeated for all reported AEs (including those reported later than 28 days after any vaccination).

Summaries of unsolicited AEs occurring within 28 days after each vaccination and within 28 days after any vaccination are provided based on the SAS 2. Summaries of all reported unsolicited AEs (including those reported later than 28 days after any vaccination) are provided based on the SAS.

Listings of unsolicited AEs and related unsolicited AEs are produced. These listings are excluding solicited AEs and flagging treatment emergent events.

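### The all-reported unsolicited-AE tables on the full SAS pool two different collection rules, so for ordinary AEs their percentages are not incidences and should be split by phase

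*SAP*

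**What the plan says.** The primary safety endpoint in SAP 9.1.2 is "Occurrence, intensity and relationship of unsolicited AEs occurring within 28 days after each trial vaccination in Phase 2b subjects". Protocol Table 9 and SAP Table 4 assign it to SAS 2, the Phase 2b subjects of the SAS. Protocol 10.2.2 gives the rule and its reason: "As solicited and unsolicited AEs are collected only for Phase 2b subjects, these analyses will then be restricted to the Phase 2b subjects".

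SAP 12.7.1.1 follows this for the 28-day tables. For the all-reported tables (any, related, by maximum severity, and the repeat of the more-than-5% PT table) it changes the set: "Summaries of all reported unsolicited AEs (including those reported later than 28 days after any vaccination) are provided based on the SAS". The all-reported overall summary in 12.7.1.3 falls to the SAS through that section's residual clause. SAP 12.7.1.4 repeats the through-EOT unsolicited tables without censoring and names no other set. SAP 12.7.7 repeats them for four groups formed by what had been received before the AE, explicitly on the SAS.

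On denominators, SAP 12.7.1 says: "In general, percentages are based on the number of subjects in the respective analysis set". The splits it specifies are vaccine group, age group and baseline serostatus, not phase.

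On collection:
- Phase 2b subjects report unsolicited AEs for 28 days after each dose. At Day 57 the site instruction reads: "Inform the subject that reporting of unsolicited AEs is complete".
- For Phase 3, Protocol 9.3.3 says that "only those AEs occurring during the 30-minute observation period after vaccination which constitute an AESI, medically-attended AE, or an SAE will be recorded".
- SAP 10.5 lists the classes collected in all subjects (medically-attended AEs, SAEs, AESIs, AEs leading to withdrawal or discontinuation) and closes: "No other AEs require recording in the CRF". Protocol 9.3.3.2 and Table 6 add intercurrent conditions that may affect the immune response.

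**The concern.** An ordinary unsolicited AE, meaning one that is not medically attended, serious, of special interest or a cause of withdrawal, has a route into the database only if the subject is in Phase 2b and within 28 days of a dose. On the SAS such events enter the numerator from about one subject in nine, while the denominator counts everyone. The printed percentage is then neither a Phase 2b incidence nor a whole-trial incidence, and nothing in the SAP text tells the reader so.

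Two things are at stake. In the randomized tables, absolute rates and risk differences for ordinary AEs are understated, and the all-reported more-than-5% PT list is shortened. In 12.7.7 the groups are not randomized. Placebo-only and CVnCoV-only contain the full-capture period and CVnCoV-AV and AV-only mostly do not, so the post-AV groups can show fewer unsolicited AEs through collection rules alone.

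**Working it through.** **Inputs.** Planned Phase 2b 4,000 and Phase 3 32,500 (Protocol synopsis, planned number of subjects). The total reproduces the stated figure: 4,000 + 32,500 = 36,500. Shares: 4,000/36,500 = 10.96%; 32,500/36,500 = 89.04%. Actual SAS counts by phase are not given.

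**Assumption.** Let m be the fraction of a given kind of unsolicited AE, within 28 days of a dose, that is also recorded in Phase 3. The documents give no value, so a range is shown. True incidence is taken as equal in the two phases and m as equal in both arms.

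**Dilution within the 28-day windows.** With true incidence q, pooled percentage = q × (4,000 + 32,500m)/36,500. The dilution factor is therefore 36,500/(4,000 + 32,500m).

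| m | factor | 10% prints as | 5-point difference prints as | Phase 2b incidence needed to pass 5% |
|---|---|---|---|---|
| 0.25 | 36,500/12,125 = 3.01 | 3.3% | 1.7 points | 15.1% |
| 0.50 | 36,500/20,250 = 1.80 | 5.5% | 2.8 points | 9.0% |
| 0.75 | 36,500/28,375 = 1.29 | 7.8% | 3.9 points | 6.4% |
| 1 | 1.00 | 10% | 5 points | 5% |

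The last column is 5% × factor. These cut-offs are upper bounds: the all-reported tables also count events after the 28-day windows, collected under the same rules in both phases. Such events raise the pooled percentage without being diluted. For the same reason the factor describes the 28-day part of a row, and a row containing many later events is diluted less.

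**What a reader could recover.** SAP 12.7.1.3 gives the 28-day overall summary on both the SAS and SAS 2. With R = SAS percentage / SAS 2 percentage, m = (36,500R − 4,000)/32,500; R = 0.55 gives m = 0.49. This works for the overall rows only. The unsolicited tables by PT are not given on both sets for the same window.

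**Time window.** Full capture runs over Days 1 to 57 (Protocol Table 6), which is 57/393 = 14.5% of the scheduled days. Afterwards both phases collect the same selected classes.

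**SAP 12.7.7.** An AE is allocated by whether an AV preceded its start date. SAP 10.5.7 regards AV receipt within the 28-day window as unlikely. The AE recording rules do not change on roll-over to the open-label phase (SAP 10.5), and "the 6 months of medically attended AE recording are not re-started when the subject receives an AV". No section re-opens ordinary unsolicited-AE collection after an AV. CVnCoV-AV and AV-only events therefore come mostly from selective-capture time in both phases. The Protocol Amendment Rationale puts AV receipt at about 49% of subjects by 18 November 2021; on the planned total, 0.49 × 36,500 ≈ 17,900.

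**The case against.** The strongest defence is that the all-reported tables are not the endpoint. The endpoint is the 28-day Phase 2b analysis, it is on SAS 2 by SOC and PT, and any PT above 5% within 28 days is shown there. Both documents use unsolicited AEs as an umbrella that includes SAEs and AESIs, and Protocol 10.3.7 foresees tabulation within 28 days and overall. An inventory of everything reported needs the SAS, because Phase 3 events belong in it.

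Much of this stands. The SAS tables have a purpose, and cutting them back to SAS 2 would drop Phase 3 events. What does not stand is printing the inventory as percentages of all SAS subjects with no split or caveat, against the rule in Protocol 10.2.2.

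A reader might also infer more than the documents support:
- **The randomized comparison is biased.** Allocation is 1:1 in both phases. If capture is equal by arm, dilution shrinks the difference but does not change its direction.
- **Rates are diluted about nine-fold.** The limit 36,500/4,000 = 9.1 applies only to event types that never meet a Phase 3 collection criterion, not to the any-AE rows.
- **The open-label safety analyses are undermined.** SAP 12.7.7 substitutes for them, but the endpoints in SAP 9.4.1 are SAEs, AESIs, fatal SAEs and, in Cohort A, AEs leading to discontinuation. Ordinary unsolicited AEs are not among them, and the SAE, AESI and fatal rows are collected in all subjects.
- **A phase split repairs 12.7.7.** It does not. After the 28-day windows the two phases are equally selective, so the post-AV columns would look alike in both.

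**Conclusion.** The point holds as a reporting fault of limited scope. The all-reported and through-EOT unsolicited-AE tables in SAP 12.7.1.1, 12.7.1.3 and 12.7.1.4 pool full and selective capture within the 28-day windows, contrary to Protocol 10.2.2 and without an entry in SAP 6.2. For ordinary AEs their percentages are not incidences. The size depends on Phase 3 capture, which is not in the documents: 3.0-, 1.8- or 1.3-fold at assumed capture of 25%, 50% or 75%, and none at 100%. These figures rest on planned enrolment, equal incidence in both phases and equal capture in both arms.

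In 12.7.7 the dominant problem is the collection window rather than phase: the any-unsolicited-AE percentages are not comparable across the four groups and can look lower after an AV for that reason alone.

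The primary 28-day analysis on SAS 2 and the SAE, AESI, fatal and medically-attended tables are unaffected by this problem. The TFL list (SAP Appendix 4) is a separate document that was not available, so a by-phase split there cannot be excluded; the SAP text specifies none.

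**What to change.** 1. In SAP 12.7.1.1, 12.7.1.3 and 12.7.1.4, present the all-reported and through-EOT unsolicited-AE tables, including the more-than-5% PT repeat, by phase with separate denominators. Keep all reported events in both columns.
2. Leave the SAE, AESI, fatal and medically-attended tables on the SAS.
3. In 12.7.7, state that ordinary unsolicited AEs were collected only in Phase 2b within 28 days of each trial dose, so unsolicited-AE percentages are not comparable across the four groups. Base comparisons there on AE classes collected in all subjects through EOT.
4. List the use of the SAS for these tables in SAP 6.2 as a departure from Protocol 10.2.2.

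The cost is SAP wording, a footnote and a phase variable in existing table programs. No new data are needed, and no reported event is removed.

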12.7.1.2 Analysis of Solicited AEs

The following summaries of solicited AEs within 7 days after each trial vaccination and within 7 days after any trial vaccination are planned:

- Summary of local and systemic AEs, overall and by maximum grade (mild / moderate / severe)
 - Also provided by gender (female/male) for any vaccination, vaccination 1, and vaccination 2.
- Occurrence of local AEs, overall and by maximum grade (mild / moderate / severe)
- Occurrence of systemic AEs, overall and by maximum grade (mild / moderate / severe)
- Occurrence of related systemic AEs, overall and by maximum grade (mild / moderate / severe)
- Duration (days) of local AEs, overall and for grade 3 events
- Duration (days) of systemic AEs, overall and for grade 3 events
- Duration (days) of related systemic AEs, overall and for grade 3 events
- Daily summary of local AEs overall and by maximum grade (mild/moderate/severe) (only for each dose)
- Daily summary of systemic AEs overall and by maximum grade (mild/moderate/severe) (only for each dose)
- Daily summary of related systemic AEs overall and by maximum grade (mild/moderate/severe) (only for each dose)
- Summary of time of onset (Day) overall and for grade 3 solicited AEs, any solicited AEs, local, systemic AEs, and related systemic AEs

- Time of onset (Day) of local AEs, overall and for grade 3 events
- Time of onset (Day) of systemic AEs, overall and for grade 3 events.
- Time of onset (Day) of related systemic AEs, overall and for grade 3 events

All analyses of solicited AEs are provided based on the SASsol.

Before EOT is was decided to not provide any analyses on solicited AEs in the EOT analysis. Therefore some of the above analyses were never performed. For details, please refer to Appendix 6.

12.7.1.3 Analysis of AEs (Combined Unsolicited and Solicited)

An overall summary of unsolicited AEs, SAEs, intercurrent medical conditions affecting immune response, AESIs, medically attended AEs, AEs leading to vaccine withdrawal, AEs leading to withdrawal from trial and AEs with fatal outcome is prepared for AEs occurring within 28 days after each CVnCoV vaccination, within 28 days after any CVnCoV vaccination, and all reported AEs (including those reported later than 28 days after any CVnCoV vaccination), presenting the number and percentage of subjects with

- any unsolicited AEs ,
- related unsolicited AEs,
- grade 3 (severe) unsolicited AEs
- grade 3 (severe) related unsolicited AEs
- SAEs (includes solicited AEs),
- related SAEs (includes solicited AEs),
- intercurrent medical conditions affecting immune response (includes solicited AEs),
- AESIs (includes solicited AEs),
- related AESIs (includes solicited AEs),
- medically attended AEs (includes solicited AEs),
- related medically attended AEs (includes solicited AEs),
- AEs leading to vaccine withdrawal (includes solicited AEs),
- AEs leading to withdrawal from trial (includes solicited AEs),
- AEs with fatal outcome (includes solicited AEs),
- related AEs with fatal outcome (includes solicited AEs).

The overall summary is also provided by gender (male/female) for any CVnCoV vaccination, CVnCoV vaccination 1 and CVnCoV vaccination 2.

The following summaries of AEs by SOC and PT are further provided, separately for AEs occurring within the first 28 days after each CVnCoV vaccination, within the 28 days after any CVnCoV vaccination, and all reported AEs (including those reported at more than 28 days after any CVnCoV vaccination):

- Occurrence of SAEs,
- Occurrence of related SAEs,
- Occurrence of SAEs by maximum severity (mild / moderate / severe),
- Occurrence of related SAEs by maximum severity (mild / moderate / severe),
- Occurrence of intercurrent medical conditions affecting immune response,

- Occurrence of AESIs,
- Occurrence of related AESIs,
- Occurrence of medically attended AEs,
- Occurrence of related medically attended AEs,
- Occurrence of AEs leading to vaccine withdrawal,
- Occurrence of AEs leading to withdrawal from trial,
- Occurrence of AEs with fatal outcome,
- Occurrence of related AEs with fatal outcome,
- Occurrence of SMQs and CMQs (as specified in Section 10.5.7). (The SMQ/CMQ tables is only provided for all reported AEs, not by vaccination 1 and vaccination 2 separately and only by PT, not by SOC.)

Overall summaries of AEs occurring within 28 days after each CVnCoV vaccination and within 28 days after any CVnCoV vaccination are provided based on the SAS and the SAS 2. Summaries of SMQs and CMQs are provided based on the SAS and the SAS 2. All other summaries and listings are provided based on the SAS.

A listing of all SAEs and all SAEs with fatal outcome is further provided by subject, including both unsolicited and solicited AEs.

Further AE listings supporting the AE tables described above include both relevant solicited and unsolicited AEs.

